8.7. Pharmacokinetic Analysis

Not applicable

8.8. Biomarker Analysis

Not applicable

8.9. Sample Size

Pediatric patients receiving Tenofovir DF may exhibit renal toxicities (e.g., proximal renal tubulopathy) among 4.5% of subjects (95% confidence band of 0.4-8.6%). Among adolescent patients with CHB, available interim 72 Week clinical trial data indicate that 5.8% (95% confidence band of 1.2-15.9%) of subjects experienced a $\geq 4\%$ decrease in BMD; by comparison 3.7% (95% CI 0.4-12.5%) of placebo controls had a BMD loss of $\geq 4\%$. In this same trial, no renal adverse drug reactions were detected by Week 72. Detecting renal or bone AEs in CHB adolescents taking Tenofovir DF are infrequent events, and the pool of Tenofovir DF-naïve subjects within the EU suitable for enrollment is limited. With a fixed sample size of 100 (50 in each monitoring group) we would expect to detect 4-5 renal or bone adverse drug reactions across both real-world groups (both receive equivalent treatment) over 96 weeks.

The study employs two monitoring protocols which specify the same laboratory and imaging tests for bone and renal markers, but differ in the frequency of testing. Group 1 will receive more frequent monitoring which is protocol-defined or SmPC specified, and Group 2 will be monitored according to a less frequent DEXA schedule for BMD and will follow the local standard of care for renal monitoring. It is hypothesized (H_0) that there will be no difference in the timing, management, or subject outcomes resulting from renal or bone AEs among the two monitoring regimens. With a one-tailed test of $\alpha=0.05$, and assuming a non-inferiority margin of 0.10, the study has at least 80% power to detect a difference between the monitoring regimens beyond the specified margin of non-inferiority.

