In a third study, 28 HIV-infected pediatric subjects (ages 5–17.9 years) receiving HAART therapy consisting of lamivudine, stavudine and a protease inhibitor (PI) with stable undetectable viral loads were randomized to switch the PI to efavirenz and stavudine to tenofovir at baseline (Group 1) or at Week 24 (Group 2). At 96 weeks, virological suppression and unchanged CD4 counts were maintained in all subjects {11526}. Tenofovir DF therapy was well tolerated. Through 96 weeks, no child experienced a Grade 1 or higher increase in serum creatinine or phosphorus, and mean serum creatinine, phosphorus and bicarbonate values were unchanged {11445}. The authors concluded that no evidence of impaired glomerular filtration or tubular renal function was observed in HIV-infected children treated with Tenofovir DF for 96 weeks. The authors also evaluated bone mineral content (lumbar spine and whole-body bone mineral content (BMC) and BMD via DEXA scan in 16 subjects in this study through 12 months of Tenofovir DF treatment {10417}. DEXA scans were obtained 12 months prior to therapy switch, at baseline, and 12 months after switch to Tenofovir DF. The authors calculated expected changes in bone measurements from data obtained from 166 healthy children. The BMC and BMD increments observed before and after switching to Tenofovir DF did not differ significantly from those calculated in healthy controls. Although the sample size is small, results from this study suggest that 12 months of Tenofovir DF treatment does not impair bone mineral accrual in HIV-infected children.

Most recently, a clinical trial of Tenofovir DF in pediatric and/or adolescent HIV-1-infected subjects is ongoing. Study GS-US-104-352 is evaluating 100 HIV-infected children and adolescents (2 to < 16 years of age) who are virologically suppressed (HIV-1 RNA < 400 copies/mL) on their current antiretroviral regimen containing either stavudine or zidovudine. Subjects are randomized 1:1 to continue on the same stavudine- or zidovudine-containing regimen, or to replace stavudine or zidovudine with Tenofovir DF while continuing their other background antiretroviral agents. The study will assess the efficacy, safety (including BMD) and tolerability of switching to Tenofovir DF, compared to continuing stavudine or zidovudine therapy. The study duration is 48 weeks. Enrollment is ongoing, with a total of 97 subjects enrolled to date.

1.3. Information about Comparator Product:

Not applicable.

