Renal toxicity associated with Tenofovir DF has been previously identified in small subsets of study participants across randomized controlled clinical trials. In an NIH systematic review of Tenofovir DF's renal safety profile, the mean difference in reduction of creatinine clearance among subjects on Tenofovir DF was 3.92 mL/min (2.13-5.70 mL/min 95% confidence interval) compared to controls, and no clear associations between treatment and proteinuria, hypophosphatemia, nor fractures. A modest increase in risk of acute renal injury (0.7%, 0.2-1.2% 95% confidence interval) was noted. The clinical impact of these findings is unknown {16177}. Among registered studies the detection on renal toxicities has been very low, ranging between 1 to 2%. Detailed information and sequelae as a result of serious renal toxicities, such as Fanconi syndrome, come from case series or single reports. A recent NIH report documented 7 of 51 (14%) adult patients treated for CHB with Tenofovir DF (and/or adefovir) who developed renal tubular dysfunction after 22 to 94 months on therapy. Subjects with renal tubular dysfunction had an average age of 58, and 6 of the 7 were male. All affected subjects had hypophosphatemia, with others having one or more indications of hypouricemia, increased serum creatinine, proteinuria, or glycosuria {20768}.

The available data to characterize the incidence of renal toxicities in children is lacking, and collected primarily within registration studies of CHB and Tenofovir DF. As Tenofovir DF also has the indication for treatment of pediatric HIV, the drug's safety profile has some overlay to both the HIV and the HBV-infected populations. Among pediatric subjects completing 144 weeks of treatment in clinical trial GS-US-104-0352, 4 of 89 (4.5%) patients discontinued Tenofovir DF treatment for HIV-1 as a result of new onset adverse reactions suggestive of PRT (e.g., glycosuria, hypophosphatemia).

Data from Collaborative HIV Pediatrics Study (CHIPS) in Ireland and the UK reported that among the 159 HIV-1 positive children taking Tenofovir DF (since 2001) of a cohort of 1253 participants, 6 (3.8%) developed renal toxicities including PRT, Fanconi syndrome, and acute renal failure. Five of the six were also taking concurrent NRTI and PI combinations, and

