Among adolescent patients with CHB, available interim 72 Week clinical trial data indicate that 5.8% (95% confidence band of 1.2-15.9%) of subjects experienced a $\geq 4\%$ decrease in BMD; by comparison 3.7% (95% CI 0.4-12.5%) of placebo controls had a BMD loss of $\geq 4\%$. In this same trial, no renal adverse drug reactions were detected by Week 72. Detecting renal or bone AEs in CHB adolescents taking Tenofovir DF are infrequent events, and the pool of Tenofovir DF-naïve subjects within the EU suitable for enrollment is limited. With a fixed sample size of 100 (50 in each monitoring group) one would expect to detect 4-5 renal or bone adverse drug reactions across both real-world groups (both receive equivalent treatment) over 96 weeks.

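### Protocol 8.9: the renal interval does not follow from 4/89, the derivation of the 4-5 expected events is not shown, and 80% power needs a true event rate of about 4.2% or less

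*Protocol*

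**What the plan says.** Protocol 8.9 gives three inputs and two conclusions.

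- **Renal rate.** Renal toxicities may occur "among 4.5% of subjects (95% confidence band of 0.4-8.6" (limits in percent). No count, denominator or source is attached. Protocol 1.4 has the only count with that rate: "4 of 89 (4.5%) patients discontinued Tenofovir DF treatment for HIV-1", described as "Among pediatric subjects completing 144 weeks of treatment in clinical trial GS-US-104-0352".
- **Bone rate.** In the trial of adolescents with chronic hepatitis B at Week 72, "5.8% (95% confidence band of 1.2-15.9%) of subjects experienced a" BMD loss of 4% or more. The placebo figure is 3.7% (0.4-12.5%).
- **Renal reactions in that same trial.** None by Week 72.
- **Expected count.** With 100 subjects over 96 weeks, "we would expect to detect 4-5 renal or bone adverse drug reactions across both real-world groups". Protocol 1.4 repeats this ("one would expect to detect 4-5 renal or bone adverse drug reactions"). Neither place shows a derivation.
- **Power.** 80% or more, one-sided alpha 0.05, non-inferiority margin 0.10, 50 per group. No event rate is stated. SAP 1.4 repeats the sentence in the past tense for the planned 100 subjects and names a spine BMD decrease of at least 4% through Week 96 as the primary safety endpoint.

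**The concern.** These are the figures a reader would use to judge what 100 subjects can show. If the interval does not come from the data, the uncertainty in the renal rate is misdescribed. If the expected count leaves out an input given in the same paragraph, the event rate is too low. Power against a fixed absolute margin falls as the event rate rises, so a low rate makes the claim look better than it is.

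The claim still matters after early termination. SAP 1.4 sets the 30 enrolled subjects against a design said to have had 80% power. A report that carries this forward would attribute the whole loss of power to low enrolment.

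**Working it through.** **1. Renal interval.** Input: 4/89 = 4.49% (Protocol 1.4).

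- Wald: p ± 1.96·√(p(1−p)/n) = 4.49 ± 1.96 × 2.196 = 0.19% to 8.80%.
- Exact (Clopper-Pearson): 1.24% to 11.11%.
- Other methods on 4/89: Wilson 1.76-10.99%, Agresti-Coull 1.41-11.35%, Jeffreys 1.54-10.33%, mid-P 1.44-10.48%, Wald with t 0.13-8.86%, Wald with continuity correction −0.37 to 9.36%.

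None gives 0.4-8.6%. To reproduce the printed figure, take p = 0.045 and vary n in the Wald formula. With n = 100 it gives 0.44-8.56%, and with n = 97 it gives 0.37-8.63%. Every n from 96 to 100 rounds to 0.4-8.6%.

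**2. Bone intervals.** The 72-week trial had 52 subjects on tenofovir DF and 54 on placebo (Protocol 1.2.3.1), so 5.8% is 3/52 and 3.7% is 2/54. Exact limits for 3/52 are 1.21-15.95% (15.947 before rounding), which reproduces the printed 1.2-15.9%. Exact limits for 2/54 are 0.45-12.75%, against the printed 0.4-12.5%, a small difference with no bearing on this point.

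**3. Expected count in 100 subjects.**

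| Reading | Renal | Bone | Total |
|---|---|---|---|
| Renal rate alone | 4.5 | – | 4.5 |
| Bone alone, Week 72 (no renal events, as in the hepatitis B trial) | 0 | 5.8 | 5.8 |
| Bone alone, scaled to 96 weeks | 0 | 7.7 | 7.7 |
| Crude renal plus bone | 4.5 | 5.8 | 10.3 |
| Both scaled to 96 weeks | 3.0 | 7.7 | 10.7 |
| Renal scaled, bone minus placebo | 3.0 | 2.1 | 5.1 |
| As above, bone excess also scaled | 3.0 | 2.8 | 5.8 |

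Scaling: renal 4.5 × 96/144 = 3.0; bone 5.8 × 96/72 = 7.7; bone excess 5.8 − 3.7 = 2.1, and 2.1 × 96/72 = 2.8. If renal and bone events are independent and subjects are counted once, the crude total is 100 × (1 − 0.955 × 0.942) = 10.0.

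**4. Power.** With equal true rates p, 50 per group, margin 0.10 and one-sided alpha 0.05:

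power = Φ(0.10/√(2p(1−p)/50) − 1.645)

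| True rate | Standard error | Power | Per group for 80% |
|---|---|---|---|
| 3.7% | 0.0378 | 84% | 45 |
| 4.2% | 0.0401 | 80% | 50 |
| 4.5% | 0.0415 | 78% | 54 |
| 5.8% | 0.0467 | 69% | 68 |
| 10.0% | 0.0600 | 51% | 112 |
| 10.3% | 0.0608 | 50% | 115 |

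The claim is met at the 3.7% placebo rate, but at neither rate that the section gives for treated patients.

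**The case against.** Several stronger readings are tempting, and the case against them is good.

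- **That the planned 100 was put in place of 89.** It fits, but so does every n from 96 to 100. Protocol 1.2.3.1, writing of what appears to be the same source study, says "Study GS-US-104-352 is evaluating 100 HIV-infected children and adolescents" and, later, "with a total of 97 subjects enrolled to date". Either figure would serve. Section 8.9 cites no count, so even the link to 4/89 rests on the matching rate.
- **That the upper limit is wrong by 2.5 points.** With 89 and the Wald method kept, it moves only from 8.6% to 8.8%. The rest of the move to 11.1% is a choice of method. The reason to prefer exact limits is that they reproduce the adjacent bone interval.
- **That the expected count is half what it should be.** The text speaks of drug reactions, which implies attribution to the drug. Subtracting placebo and scaling for time gives about 5-6, close to 4-5. This stands as a possible reading, but the protocol does not state it. Protocol 8.1.2 counts a BMD loss of 4% or more within the primary endpoint without placebo correction, and a comparison of monitoring groups counts observed events.
- **That these figures are the whole case for 100 subjects.** Section 8.9 also says that the pool of eligible patients is limited. It calls the size fixed, and the renal interval does not enter the power calculation.

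The SAP says openly that 30 enrolled subjects are too few and that the data will be described. That lowers the practical stakes, but it does not correct the claim made for 100.

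**Conclusion.** Three narrower statements hold. The printed renal interval does not follow from 4/89 by any of the eight standard methods tried, and its denominator is not stated. The count of 4-5 matches the renal rate alone, while the crude rates in the same paragraph give about 10 per 100; only an unstated placebo-corrected, time-scaled reading comes near 5. Power of 80% or more requires a true rate of about 4.2% or less. It is 78% at 4.5%, 69% at 5.8% and about 50% at a combined rate of about 10%.

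The power figures assume equal true rates, the unpooled normal approximation and complete follow-up of 50 per group. Section 8.9 does not say which endpoint carries the 0.10 margin. The 5.8% is the rate closest in kind to the SAP's primary safety endpoint, although 8.9 does not say whether it refers to spine or whole body. The combined rate applies only if a renal-or-bone composite is meant.

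A reader might infer that none of the inputs reproduce, or that the sample size should change. The documents support neither: the tenofovir DF bone interval reproduces exactly, and 100 is a fixed number.

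**What to change.** - **Protocol 8.9, renal interval.** State the count, denominator and method. If the source is 4/89, exact limits of 1.2-11.1% would match the method of the adjacent bone interval. If another denominator was used, name it.
- **Protocol 8.9 and 1.4, expected count.** Show the derivation: about 6 per 100 for bone alone at Week 72, or about 10 for crude renal plus bone. If a drug-attributable excess is meant, label it so and give about 5-6.
- **Protocol 8.9 and SAP 1.4, power.** Name the endpoint and the assumed event rate: about 69% at 5.8% for BMD loss, or about 50% if the renal-or-bone composite is meant.

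The changes are to text only. N stays at 100, and neither data collection nor the analysis is affected. The cost is a less favourable stated power.

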8.6. Safety Analysis

All safety data collected on or after the date that Tenofovir DF was first dispensed up to the date of last dose of Tenofovir DF will be summarized by monitoring group. Data for any pre-treatment and treatment-free follow up periods will be included in data listings.

The primary safety analysis will be performed after the last assigned subject reaches Week 96. The analysis will evaluate the difference between renal or bone AEs recorded within each of the monitoring groups with respect to the primary safety endpoint, estimating the cumulative incidence proportions using time-to-event methodology and performing comparisons using 95% confidence intervals for differences in proportions.

The proportion of subjects in each monitoring group with renal or bone AE leading to permanent discontinuation of Tenofovir DF through Week 96 will be summarized. Descriptive statistics such as n, mean, standard deviation, median, Q1, Q3, minimum and maximum) by monitoring group will be used to report demographics and time to event summaries, and a Wilcoxon rank sum test may be used to compare AEs between monitoring groups.

For categorical safety data including incidence of AEs and categorizations of laboratory data, a Fisher's exact test will be used to compare monitoring groups. For continuous safety data including laboratory data, a Wilcoxon Rank sum test will be used to compare monitoring groups. Subgroup analyses of safety endpoints will include analyses by assigned monitoring group, age groups, and geographical location of study site.

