8.6.4. Other Safety Evaluations: Analyses of BMD

Cumulative incidence of at least a 4% decrease from baseline in BMD (spine BMD and whole body BMD) using time-to-event methodology will be summarized and compared between treatment groups using 95% confidence intervals for difference in person time rates.

The percent change from baseline in BMD (spine BMD and whole body BMD) will be summarized over time and compared between treatment groups using the Generalized Linear Model. Lumbar spine and whole body z-scores (derived from DEXA-derived BMD assessments) and the changes in z-scores from Baseline will be summarized.

BMD (via DEXA scan) and serum bone biochemical markers will be summarized over time. Changes from study baseline in bone biochemical markers will also be summarized after adjusting for potential confounders such as age and gender..

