1.4. Sample Size and Power

Planned Sample Size	100 subjects (50 subjects to one of two monitoring groups)
Power Statement	
The study employed two monitoring protocols which specified the same laboratory and imaging tests for bone and renal markers and differed in the frequency of testing. Group 1 receives more frequent monitoring which is protocol-defined or SmPC specified, and Group 2 subjects are monitored according to a less frequent DXA schedule for BMD and followed the local standard of care for renal monitoring. It is hypothesized (H_0) that there would have been no difference in the timing, management, or subject outcomes resulting from renal or bone AEs among the two monitoring regimens. With a one-tailed test of $\alpha=0.05$, and assuming a non-inferiority margin of 0.10, the study had at least 80% power to detect a difference between the monitoring regimens beyond the specified margin of non-inferiority.
 
The primary safety endpoint is cumulative incidence of at least a 4% decrease from study baseline (BL) in spine bone mineral density (BMD) through Week 96.
 
The null hypothesis is the difference (Group 1 – Group 2) is equal to 0.
 
The alternative hypothesis is the difference (Group 1 – Group 2) is not equal to 0.

Actual Enrollment and Impact on Power	
The study failed to achieve its targeted enrollment of 100 patients, 50 per monitoring group. The study was discontinued as a result of the recent approval of Tenofovir alafenamide fumarate (TAF) medicine which offers a safer treatment option for CHB patients and due to low subject enrollment after the CHMPs assessment of the 18 month interim enrollment report. At the time of its closure the study enrolled 30 patients, 15 per monitoring group. The total enrolled subjects are underpowered to statistically detect differences in outcomes between monitoring groups.

--	--

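### The stated 80% power belongs to a one-sided 0.05 margin test, but the planned group comparisons use 95% intervals, at which power is about 57-75% at the protocol's own event rates

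*Protocol*

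**What the plan says.** Protocol 8.9 gives a one-tailed test at alpha 0.05 and continues: "assuming a non-inferiority margin of 0.10, the study has at least 80% power". It attaches no event rate, endpoint, direction or unit to that claim. Earlier in the same section it quotes 4.5% for renal toxicity, 5.8% for a BMD loss of at least 4% on tenofovir DF and 3.7% for the same loss on placebo. It adds that, with 50 subjects per group, "we would expect to detect 4-5 renal or bone adverse drug reactions across both real-world groups".

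SAP 1.4 repeats the claim in the past tense: "assuming a non-inferiority margin of 0.10, the study had at least 80% power to detect a difference". It then states a null of zero difference between the groups against a two-sided alternative, with no margin.

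The analysis sections use a different level. Protocol 8.6, on the primary safety analysis, plans "performing comparisons using 95% confidence intervals for differences in proportions". Protocol 8.6.4, on the cumulative incidence of a BMD decrease of at least 4%, has the groups "compared between treatment groups using 95% confidence intervals for difference in person time rates". No 90% interval is planned anywhere. No section says which confidence limit is to be set against 0.10, or by which interval method.

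**The concern.** A one-sided 0.05 non-inferiority test is the same as asking whether the upper limit of a two-sided 90% interval lies below the margin. Asking it of a 95% interval is a one-sided 0.025 test. The plan states its power for the first and plans intervals that correspond to the second.

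Section 8.6.4 adds a mismatch of scale. Its interval is for a difference in person-time rates, while the 0.10 appears beside event proportions and the stated power is reproduced only approximately, by treating it as a difference in proportions. An interval on one scale cannot be compared with a margin on another.

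At stake is whether the 80% describes the analysis that was planned, and whether a reader could tell from the protocol what result would have counted as non-inferior.

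**Working it through.** **Inputs.** From Protocol 8.9: n = 50 per group, margin 0.10, one-sided alpha 0.05, power at least 80%, rates 3.7%, 4.5% and 5.8%, and 4-5 events expected in total. From Protocol 8.6 and 8.6.4: 95% intervals.

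**Assumptions.** The margin is a difference in proportions. True rates are equal in the two groups. There is no dropout, since none is stated. Power means the chance of showing non-inferiority. The direction is Group 2 minus Group 1, because the plan names none.

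**Step 1: formula.** With common rate p,

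SE = √(2p(1−p)/50), power = Φ(0.10/SE − z),

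where z = 1.645 for one-sided 0.05 and 1.960 for one-sided 0.025.

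**Step 2: reproduce the stated figure.** At p = 4%, SE = √(2 × 0.04 × 0.96/50) = 0.0392 and 0.10/0.0392 = 2.552. Power = Φ(2.552 − 1.645) = 81.8%. So the claim is reproduced at one-sided 0.05 for a rate near the low end of the expected 4-5 events per 100. Solving for 80% gives a common rate of 4.2% or less.

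**Step 3: both levels at the quoted rates.**

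| Rate | SE | 0.10/SE | Power, one-sided 0.05 | Power, 95% interval | n per group for 80%: 0.05 / 0.025 |
|---|---|---|---|---|---|
| 3.7% | 0.0378 | 2.649 | 84% | 75% | 45 / 56 |
| 4.5% | 0.0415 | 2.412 | 78% | 67% | 54 / 68 |
| 5.8% | 0.0467 | 2.139 | 69% | 57% | 68 / 86 |

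The last column is (z + 0.842)² × 2p(1−p)/0.10², rounded up. At one-sided 0.025 with 50 per group, 80% power needs (1.960 + 0.842) × SE ≤ 0.10, that is p of about 3.3% or less.

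**Step 4: can the conclusion differ at the expected counts?** Take 5 events, 2/50 in Group 1 and 3/50 in Group 2. The difference is 0.02 and the Wald SE is √(0.04 × 0.96/50 + 0.06 × 0.94/50) = 0.0435.

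- 90% upper limit: 0.02 + 1.645 × 0.0435 = 9.2%, below the margin.
- 95% upper limit: 0.02 + 1.960 × 0.0435 = 10.5%, above it.

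So it can. I then took all 11 splits of 4 or 5 events, in both directions:

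- Wald: only 2 v 3 differs.
- Newcombe: none differs (2 v 3 gives 10.5% and 12.6%, failing at both levels).
- Agresti-Caffo: 2 v 3 only, and only at rounding (10.00% and 11.55%).
- Miettinen-Nurminen: 2 v 2 only (7.97% and 10.06%).

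**Step 5: how often over all outcomes.** With equal true rates of 3.7-5.8%, the exact binomial chance that the two levels disagree is 5-10% by Wald, 15-16% by Newcombe, 16-18% by Agresti-Caffo and 20-24% by Miettinen-Nurminen.

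**The case against.** The strongest reply is that no section ties the 95% interval to the margin. Sections 8.6 and 8.6.4 mention neither non-inferiority nor 0.10, and reporting a 95% interval beside a one-sided 5% test is common practice. This stands. The plan does not apply the stricter rule; it states no rule, and the power at 0.025 is what follows if the margin is read from the only between-group intervals it plans. Nor does the sample size settle which level was meant: 4.2% and 3.3% both lie inside the wide confidence bands that 8.9 gives for its rates.

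Three stronger readings are tempting, and the documents do not support them.

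- *That the conclusion generally flips at the event counts the plan expects.* The expected 4-5 events are a total over both groups. A split of 4 v 4, which does flip by all four methods, is eight events; at a 4.5% rate the chance of eight or more among 100 is about 8%. At 4-5 events a flip is the exception and depends on the split and on an unnamed method.
- *That 8.6.4 turns the margin into 0.10 per person-year.* On a 5.8% base over 96 weeks (1.84 years) that would allow an excess of about 15.8 percentage points, but no section reads the margin that way. What stands is only that the interval and the margin are on different scales.
- *That the final report will draw a wrong conclusion.* SAP 1.4 says the 30 enrolled are too few to detect differences, SAP 2.1 turns to description, and SAP 7.3 rules out inferential statistics for the BMD incidence.

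**Conclusion.** The mismatch is real and limited. The claim of at least 80% power is tied to one-sided 0.05. Even there it holds at 3.7% but not at 4.5% or 5.8%. Read from the planned 95% intervals, power is about 75%, 67% and 57%, a loss of 9 to 12 percentage points, and none of the three quoted rates reaches 80%. These figures rest on the normal approximation, equal true rates, 50 per group, no dropout and a margin on the difference in proportions.

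The 95% interval is the stricter rule, so a reader should not infer inflated type I error. The harm is an overstated power figure and a decision rule that was never written down. SAP 1.4 carries the figure forward and adds a two-sided null of zero difference that does not match a margin test. SAP 7.8 says the protocol-specified safety analysis is unaltered, so the record still points to the 95% intervals. Correcting this changes the stated design and power; it changes no conclusion from the data on the 30 enrolled.

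**What to change.** - Use one error level for the margin comparison. Either keep the 95% intervals and state one-sided 0.025 in Protocol 8.9 and SAP 1.4, or keep one-sided 0.05 and name a 90% interval for the margin test. Both are coherent.
- Restate the power at that level with its assumed event rate: about 57-75% at 0.025, or 69-84% at 0.05, over rates of 5.8% down to 3.7%.
- Set 0.10 against the difference in 96-week cumulative incidence, naming the endpoint, the direction and the interval method. Keep the person-time rate difference in 8.6.4 as descriptive.
- In SAP 1.4, reconcile the two-sided null of zero difference with the non-inferiority statement.

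The cost is wording in Protocol 8.6, 8.6.4 and 8.9 and in SAP 1.4, plus a less favourable power figure. No data or subjects are needed to correct the record. Delivering 80% at 0.025 would have taken 56 to 86 per group at the quoted rates.
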